1. PREVIOUS STUDY HISTORY

Has this study ever been reviewed and rejected/disapproved by another IRB prior to submission to this IRB?

No Yes – if yes, please explain: |

2. BRIEF SUMMARY OF RESEARCH

- *The summary should be written in language intelligible to a moderately educated, non-scientific layperson.*
- *It should contain a clear statement of the rationale and hypothesis of your study, a concise description of the methodology, with an emphasis on what will happen to the subjects, and a discussion of the results.*
- *This section should be ½ page*

Peripheral arterial disease (PAD) affects approximately 10% of the American population, with 30% to 40% of these patients presenting with claudication symptoms. The prevalence of PAD increases with age and the number of vascular risk factors. More importantly, it is a marker of atherosclerotic disease burden, and is associated with increased mortality from cardiovascular and cerebrovascular causes. There have been recent advances in noninvasive imaging, endovascular approaches for revascularization, and aggressive risk factor management for prevention of cardiac and cerebrovascular complications in PAD.

Ultrasound scanning imaging systems are currently the primary choice for vascular diagnostics. After a standard vascular study, the ultrasound technologist produces a handwritten sketch that highlights various parameters (vessel size and blood flow) throughout the vasculature in question. This sketch is then interpreted by the physician who then assesses and, if need be, performs interventions. This sketch is shown to the patient to better illustrate the vascular insufficiency issues that are affecting the patient. A digital copy of the sketch is also uploaded to the patient portal.

Due to a limited field of action and poor quantification accuracy, patients are often referred for secondary scanning procedures such as computed tomography angiography, magnetic resonance angiography and catheter angiography for more detailed imaging. Referrals delay treatment, expose the patient to potential health risks and pose higher costs to healthcare providers. This can lead to poor patient compliance and avoidable hospital readmissions. This presents a need to improve the rapidity and safety of the diagnosis of vascular conditions in patients to enable rapid treatment of conditions such as peripheral artery disease. There is also a need for cost effective preventative screening and surveillance to enable early intervention, for example, people at high risk of limb amputation.

The ability to have a visual aid to depict areas of vascular disease that are affecting the patient's health can help in patient comprehension of the problem. This comprehension can lead to better understanding of the issue and increase patient compliance to treatment. The hand drawn sketch produced by the ultrasound technologist provides an inadequate visualization of the vascular insufficiency that is causing the patient's symptoms.

PIUR imaging has developed PIUR Infinity tUS, a 3D freehand tomographic ultrasound system capable of rapid, safe and accurate reconstructive 3D quantifiable vascular imaging. This system will provide a low cost and reproducible imaging solution that will be an effective educational tool for people with vascular disease. |

3. INTRODUCTION/BACKGROUND MATERIAL/PRELIMINARY STUDIES AND SIGNIFICANCE

- *Describe and provide the results of previous work by yourself or others, including animal studies, laboratory studies, pilot studies, pre-clinical and/or clinical studies involving the compound or device to be studied.*
- *Include information as to why you are conducting the study and how the study differs from what has been previously researched, including what the knowledge gaps are.*
- *Describe the importance of the knowledge expected to result*

The PIUR tUS Imaging System has been approved for use in the European Union for over 1 year. Studies performed in Europe have highlighted the system's ability to accurately depict various pathologies in a 3D form. Currently, there is no market equivalent of this technology approved by the FDA for use in the United States. We are conducting this study to determine whether the 3D images created by the device shown to patients can be used as an educational tool to increase patient comprehension of the disease process, compared with the standard of care 2D images. This will be measured in terms of compliance with follow-up appointments and 30-day readmission rates. |

4. OBJECTIVE(S)/SPECIFIC AIMS AND HYPOTHESES

- *A concise statement of the goal(s) of the current study.*
- *The rationale for and specific objectives of the study.*
- *The goals and the hypothesis to be tested should be stated.*

The objective of this study is to compare readmission rates and compliance with follow-up appointments among patients who are shown the 3D rendering of their ultrasound compared with a historical cohort of patients who viewed 2D based sketches of their vasculature. We hypothesize that patients receiving the 3D ultrasound would have higher compliance with follow-up appointments and lower

readmission rates compared with patients who did not have a 3D rendering of their study created because patients in the 3D subset would be better able to visualize their affected blood vessels and understand disease severity.

5. RESOURCES AVAILABLE TO CONDUCT THE HUMAN RESEARCH

- *Explain the feasibility of meeting recruitment goals of this project and demonstrate a potential for recruiting the required number of suitable subjects within the agreed recruitment period*
 - *How many potential subjects do you have access to?*
- *Describe your process to ensure that all persons assisting with the trial are adequately informed about the protocol and their trial related duties and functions*

The wound center has a vascular suite in which 10-15 vascular ultrasound tests are performed on a daily basis. The vascular suite has its own ultrasound machine. Potential subjects will be recruited from the pool of patients who have been scheduled to undergo ultrasound testing of their vasculature. The ultrasound technologists will be instructed in how to use the device. The method and technique of performing the test will not be altered in any way. The tech will perform the standard vascular testing as designated by the clinician who ordered the test.

6. RECRUITMENT METHODS

- *Describe the source of potential subjects*
- *Describe the methods that will be used to identify potential subjects*
- *Describe any materials that will be used to recruit subjects. A copy of any advertisements (flyers, radio scripts, etc.) should be submitted along with the protocol.*
- *If monetary compensation is to be offered, this should be indicated in the protocol*

Participants will be recruited from the wound center's patient population. The wound center's vascular suite performs 10-15 ultrasound studies on a daily basis. These patients are experiencing symptoms of vascular insufficiency. There are various anatomical locations that are studied with ultrasound and therefore subjects will be grouped for analysis. These patients will be approached to enroll in the study. No materials will be used to recruit subjects. Subjects will not be offered compensation to participate.

7. ELIGIBILITY CRITERIA

- *Describe the characteristics of the subject population, including their anticipated number, age, ranges, sex, ethnic background, and health status. Identify the criteria for inclusion or exclusion of any subpopulation.*
- *Explain the rationale for the involvement of special classes of subjects, such as fetuses, pregnant women, children, prisoners or other institutionalized individuals, or*

others who are likely to be vulnerable. You cannot include these populations in your research, unless you indicate such in the protocol

- *Similarly, detail exclusionary criteria: age limits, special populations (minors, pregnant women, decisionally impaired), use of concomitant medications, subjects with other diseases, severity of illness, etc.*

INTERVENTIONAL COHORT:

Inclusion:

- Age 18 years of age or older
- Suspected vascular insufficiency that requires ultrasound evaluation
- Subject is able to sign a consent form
- Scheduled ultrasound testing at the wound center to evaluate vasculature

Exclusion:

- Younger than 18 years old
- Subject is not scheduled to have ultrasound testing at the wound center
- Subject is unable to or refuses to consent to participate

RETROPECTIVE COHORT:

Inclusion:

- Age 18 years of age or older
- Subjects who have undergone vascular ultrasound testing at the wound center
- Ultrasound tests performed from 1/1/2019-12/31/2019
- Subjects who were followed by the wound center team after undergoing ultrasound testing for vascular insufficiency

Exclusion:

- Younger than 18 years old
- Subjects who underwent testing outside the above mentioned timeframe
- Subjects who were not followed by the wound center team after undergoing ultrasound testing for vascular insufficiency

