12. STATISTICAL ANALYSIS

- *Describe how your data will be used to test the hypotheses.*
- *State clearly what variables will be tested and what statistical tests will be used.*
- *Include sample size calculations.*
- *If this is a pilot study, state which variables will be examined for hypothesis generation in later studies.*

Patients who consent to have 3D imaging of their study rendered will be shown the computer animation in addition to the handwritten sketch traditionally used by vascular surgeons. We will then compare outcomes such as 30-day re-admission rates and compliance to follow-up appointments. Ultrasound types will be grouped for analysis (lower extremity to lower extremity, upper extremity to upper extremity, etc).

The primary analysis will compare the proportion of patients readmitted within 30 days of their ultrasound among those who received the 3D ultrasound vs. those who received the 2D ultrasound using a chi-square test. We will also compare the proportion of patients who showed up for their follow-up appointment among those who received the 3D ultrasound vs. those who received the 2D ultrasound using a chi-square test. We will assess for differences in baseline characteristics and factors known to be associated with readmission and compliance with follow-up among the two groups. If warranted, we will adjust for these differences using multivariable regression models.

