20. PROVISIONS TO PROTECT PRIVACY INTERESTS OF SUBJECTS

- *Describe the methods used to identify potential research subjects, obtain consent and gather information about subjects to ensure that their privacy is not invaded.*
- *In addition consider privacy protections that may be needed due to communications with subjects (such as phone messages or mail).*

Potential research subjects will be identified from the patient pool scheduled to undergo ultrasound testing at the wound center. Participant data will not be collected until the subject is consented. Study personnel will not have to communicate with subjects once their imaging study is complete.

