 - *Describe the process for assent of subjects; indicate whether assent will be required of all, some or none of the subjects. If some, which subjects will be required to assent and which will not.*
 - *If assent will not be obtained from some or all subjects, provide an explanation as to why not*
 - *Describe whether assent will be documented and the process to document assent*

- *Indicate if the subject could regain capacity and at what point you would obtain their consent for continued participation in the study*

N/A

If the study will enroll non-English speaking subjects:

- *Indicate what language(s) other than English are understood by prospective subjects or representatives*
- *Indicate whether or not consent forms will be translated into a language other than English*
- *Describe the process to ensure that the oral and written information provided to those subjects will be in that language*
- *If non-English speaking subjects will be excluded, provide a justification for doing so*

Spanish consents will be made available for potential subjects who are Spanish-speaking.
--

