24. WAIVER OR ALTERATION OF THE CONSENT PROCESS

N/A

Complete this section if you are seeking an alteration or complete waiver of the consent process.

- *Describe the possible risks of harm to the subjects involved in this study and explain why the study involves no more than minimal risk to the subject:*
- *Explain why the waiver/ alteration will not adversely affect the rights and welfare of subjects*
- *Explain why it is impracticable to conduct this research if informed consent is required*
- *Explain why it is not possible to conduct this research without using the information or biospecimens in an identifiable form*
- *If appropriate, explain how the subjects will be provided with additional pertinent information after participation. If not appropriate to do so, explain why.*

In regards to the RETROSPECTIVE COHORT:

This study poses minimal risk of harm to subjects within this cohort as the intervention to be studied has already occurred. The subject consented to undergoing the vascular study at that time. Our research team will access these subject charts to collect information regarding the results and outcomes of these subjects after their vascular studies were performed.

The waiver of consent will not adversely affect subject's rights and welfare because there is no clinical intervention and/or assessment being made on these subjects. The intervention in question has already been performed on the

subject to which they consented to at the time of the procedure. Inclusion in the study will not affect their care in any form.

Requiring informed consent for this cohort would be impracticable because many subjects who qualify for this cohort are no longer under the care of the researchers. In addition, tracking down and locating these subjects in order to have a consent form delivered and signed would create a significant logistical challenge. Finally, the creation of a consent form would then create the only traceable paper trail linking the subjects to the study. All other records of these subjects are digitized and will be accessed via EMR.

Identifiable information is required to perform the data collection. To ensure accuracy and quality of the data, subject records may be accessed more than once. Once the data collection phase is complete, all identifiers will be permanently erased from the database. The final dataset to be analyzed will not contain any PHI.

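### Section 7 requires ability and willingness to consent of the 3D cohort only, which may bias the unadjusted readmission comparison toward 3D by an unknown amount

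*Protocol*

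**What the plan says.** Section 7 lists criteria for each cohort separately. For the 3D (interventional) cohort, one inclusion criterion is "Subject is able to sign a consent form", and one exclusion is "Subject is unable to or refuses to consent to participate". The retrospective 2D criteria mention neither capacity nor consent. Section 24 asks for a waiver for that cohort and argues that "The waiver of consent will not adversely affect subject's rights and welfare".

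The 2D cohort has a filter of its own. Section 7 excludes "Subjects who were not followed by the wound center team after undergoing ultrasound testing for vascular insufficiency", and the 3D cohort has no such condition.

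Section 12 states: "The primary analysis will compare the proportion of patients readmitted within 30 days of their ultrasound", by chi-square test and without covariates. Differences in baseline characteristics and known prognostic factors are to be examined, and then: "If warranted, we will adjust for these differences using multivariable regression models". Section 20 adds that "Participant data will not be collected until the subject is consented".

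**The concern.** The study attributes any difference in readmission to the image shown. There is no randomisation and no concurrent control, so a difference in who may enter each cohort passes straight into the primary result. Ability and willingness to consent could well be related to health and engagement with care. If patients who cannot or will not consent are readmitted more often, removing them from the 3D cohort alone lowers the 3D rate even when the image does nothing.

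The planned adjustment is a weak safeguard here, for three reasons:
- It is conditional.
- Every 3D patient has capacity, so a 2D patient without it has no 3D counterpart and a model can only extrapolate.
- Willingness to join a study was never recorded for 2019 patients, and Section 20 rules out participant data on 3D-period patients who decline.

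**Working it through.** **The plan's own figure.** Section 8 assumes 10% (2D) against 2% (3D), a stated 80% (taken as power) and 95% confidence (taken as two-sided 0.05). The unpooled normal approximation gives

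n = (1.960 + 0.842)² × (0.10×0.90 + 0.02×0.98) / 0.08² = 134.4, rounded up to 135 per group.

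This matches Section 8, and the sample size is not in dispute.

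**Effect of the consent filter on readmission.** The documents give neither a consent rate nor outcomes for non-consenters, so both are assumed. Let q be the share of the source population who would not or could not consent, and r their readmission risk relative to consenters. Take no effect of the image, and take the 10% of Section 8 as the rate in a 2D cohort without a consent filter. The effect of the followed-only restriction on readmission is ignored. The 3D rate is then

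p = 0.10 / [(1 − q) + q×r].

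For example, q = 0.2 and r = 2 gives 0.10/1.2 = 8.3%. The chance of a significant chi-square at 135 per group comes from exact binomial probabilities for p against 10%.

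| q | r | 3D rate | Spurious difference (points) | Significant in favour of 3D | Significant, either direction |
|---|---|---|---|---|---|
| none | – | 10.0% | 0 | 2.5% | 5.1% |
| 0.1 | 1.5 | 9.5% | 0.5 | 3.4% | 5.3% |
| 0.2 | 2 | 8.3% | 1.7 | 6.9% | 7.7% |
| 0.3 | 3 | 6.3% | 3.8 | 20.3% | 20.4% |
| 0.5 | 3 | 5.0% | 5.0 | 34.6% | 34.6% |

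The planned difference is 10 − 2 = 8 points, so the range of 0.5 to 5.0 points is about 6% to 63% of it.

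For consent selection alone to produce the full 2% against 10%, (1 − q) + q×r must equal 5, so r = [5 − (1 − q)]/q. That is 14.3 at q = 0.3 and 9 at q = 0.5. Selection on consent is therefore unlikely to explain the whole planned effect.

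**Attendance.** Two filters act in opposite directions. Assume 80% attendance in the source and 20% non-consenters who attend 0.8 times as often as consenters.
- Consent filter: 3D becomes 0.80/(0.8 + 0.2×0.8) = 83.3%, which is 3.3 points above an 80% 2D cohort.
- If the followed-only rule drops half of the 2D non-attenders, 2D becomes 0.80/(0.80 + 0.10) = 88.9%, and the difference is −5.6 points.
- If it drops all of them, 2D is 100%, and the difference is −16.7 points.

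The sign depends on how being followed is applied, so no net direction can be claimed.

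**The case against.** Consent in a prospective arm and a waiver in a chart-review arm come with the historical-control design, and every input to the size is assumed. Both points are true. They limit how strongly the point can be put, but the chart-readable part of the mismatch is still cheap to remove.

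Four stronger readings are tempting, and the documents do not support them.

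- *The 2D cohort is all comers.* It is not: Section 7 admits only patients followed by the wound center. For the same reason a reader cannot conclude that 3D is favoured on attendance as well as readmission.
- *The 2D cohort contains patients without capacity.* This is not established. Section 24 says that the retrospective subjects consented to the clinical scan, and the vulnerable-populations entry in Section 26, whose list includes cognitive impairment, is N/A. Neither settles it, since a surrogate may have consented and check marks may not have survived text extraction. What stands is that no capacity criterion is written for 2D.
- *Speakers of languages other than English or Spanish are excluded from 3D.* Section 23 says only that "Spanish consents will be made available for potential subjects who are Spanish-speaking", and Section 7 has no language criterion.
- *Regression cannot help.* Age, comorbidity and similar measured correlates may remove part of the bias. The argument from lack of overlap applies to capacity, and the argument from lack of measurement applies to willingness.

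It is also fair to say that the assumed non-consent share mixes those unable and those unwilling, while the remedy reaches only the first group. If most non-consent is refusal, the remedy removes little of the bias.

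**Conclusion.** The point holds in a limited form. The cohorts are selected by different rules, and the primary readmission test is unadjusted. A bias toward 3D on readmission follows if non-consenters are at higher risk, which the documents neither state nor contradict. Under the assumptions above the spurious difference runs from about 0.5 to 5 points, and the chance of a falsely significant benefit rises from 2.5% to between 3.4% and 34.6%. The true size is unknown and could be at or below the low end. The net effect on attendance is unsigned. The conditional regression should not be relied on to remove the bias, although it may reduce it. This is an inexpensive improvement to eligibility and record-keeping. It does not show that a positive result would be spurious.

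**What to change.** In Section 7, add to the retrospective cohort an exclusion for documented lack of decision capacity or a surrogate decision maker at the time of the scan. Do not exclude by recorded language unless the 3D cohort is given the same written rule; otherwise a new mismatch is created.

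For the 3D enrolment period, keep a log of the number of patients approached, unable to consent and declining, by ultrasound type. Because it holds counts and no patient data, it is compatible with Section 20. Use it in a sensitivity analysis that replaces the assumed q by the observed share. The relative risk r will still have to be assumed, so state it and vary it.

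State as a limitation that selection by refusal cannot be matched in 2019 charts. The followed-only restriction on the 2D cohort is a separate mismatch that this change does not remove.

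The cost is one exclusion line, some chart abstraction, a tally sheet and a slightly narrower control population. Supply should not be a problem: at the 10-15 scans a day given in Sections 5 and 6, 135 scans is 9 to 13.5 days of activity, assuming similar volume in 2019 and before the other criteria are applied.

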8. NUMBER OF SUBJECTS

- *Indicate the total number of subjects to be accrued locally. If applicable, distinguish between the number of subjects who are expected to be pre-screened, enrolled (consent obtained), randomized and complete the research procedures.*
- *If your study includes different cohorts, include the total number of subjects in each cohort.*
- *If this is multisite study, include total number of subjects across all sites.*

The total number of subjects we plan to enroll is 270. We plan to enroll 135 subjects into the 3D imaging cohort of this study. Another 135 patients will be identified retrospectively for the historical cohort.

The sample size calculation was based on the primary outcome of 30-day readmission. We assumed a readmission rate of 10% in the 2D group and a readmission rate of 2% in the 3D group. We would need 135 patients in each group to have 80% and a confidence level of 95% to detect this difference.

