9. STUDY TIMELINES

- *Describe the duration of an individual's participation in the study*
- *Describe the duration anticipated to enroll all study subjects*
- *The estimated date of study completion*

The duration of an individual's participation will last as long as it takes to perform their scheduled ultrasound testing. Ultrasound testing usually takes no more than 30 minutes. Enrolled subject's EMR will be reviewed for 6 months after they undergo the ultrasound testing. We anticipate it will take 6-8 months to enroll all study subjects.

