10. ENDPOINTS

- *Describe the primary and secondary study endpoints*
- *Describe any primary or secondary safety endpoints*

The primary endpoint of the study will be the treatment outcomes for the patients. We will review readmission rates (30 days from the day of the ultrasound) as well as compliance to first follow-up appointment after the ultrasound of interventional cohort. These endpoints will be compared to those of a historical cohort of persons who were treated for similar pathologies in the past.

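### 2D controls may come from any month of 2019 while 3D patients are enrolled over 6-8 months; limiting controls to the same calendar months would remove a possible, probably modest, seasonal imbalance

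*Protocol*

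**What the plan says.** Protocol Section 7 sets the time window for the retrospective cohort: "Ultrasound tests performed from 1/1/2019-12/31/2019". Section 9 gives the length of prospective recruitment, but not its calendar months: "We anticipate it will take 6-8 months to enroll all study subjects". Section 8 adds "Another 135 patients will be identified retrospectively for the historical cohort", without saying how those patients are drawn from the year.

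Section 10 names two outcomes: "readmission rates (30 days from the day of the ultrasound") and "compliance to first follow-up appointment after the ultrasound of interventional cohort". Section 12 compares each between cohorts with a chi-square test and calls the readmission comparison the primary analysis. It also provides for multivariable regression if baseline characteristics, or factors known to affect the outcomes, turn out to differ. Neither month nor season is named there, and no section matches, restricts or stratifies controls by calendar month.

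**The concern.** The comparison is not randomised and uses a historical control, so its credibility depends on how the controls are chosen. Both outcomes occur soon after the scan, and so fall at a time of year fixed by the scan date. If admissions or kept appointments rise and fall over the year, a cohort covering half to two-thirds of a year is being compared with one that may cover all of it. The resulting difference would have nothing to do with the 3D images, and its sign would depend on when recruitment began.

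This is distinct from the gap in years between the cohorts. A more recent 12-month control window would leave it in place, whereas selecting scans by month would deal with it.

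**Working it through.** **Inputs from the protocol.** Control window of 12 months (Section 7); 3D enrolment of 6-8 months (Section 9); 135 per group, readmission of 10% in the 2D group and 2% in the 3D group, 80% power, 95% confidence (Section 8); chi-square test (Section 12); 10-15 scans a day (Section 5).

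**Inputs assumed.** Two-sided 5% test; a cosine-shaped yearly cycle; relative swings of 20% and 30% around 10% readmission; controls spread evenly over 2019; no device effect; 21 working days a month. None of these is in the protocol.

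**1. The protocol's sample size.** Normal formula with unpooled variance:

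n = (1.960 + 0.842)² × (0.10×0.90 + 0.02×0.98) / 0.08² = 7.849 × 0.1096 / 0.0064 = 134.4, rounded up to 135.

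This matches Section 8. The exact power of the Pearson chi-square test at 135 per group is 83.1%.

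**2. Shift from a part-year window.** The mean of a cosine over w months centred on its peak or trough is f = sin(πw/12)/(πw/12). This gives f = 0.637 for 6 months and 0.413 for 8 months. Over 12 months f = 0, so evenly spread controls sit at the annual mean. The worst-phase shift in the 3D rate is 10% × swing × f:

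- 20% swing: 10 × 0.20 × 0.637 = 1.27 points (6 months); 10 × 0.20 × 0.413 = 0.83 points (8 months).
- 30% swing: 10 × 0.30 × 0.637 = 1.91 points (6 months); 10 × 0.30 × 0.413 = 1.24 points (8 months).

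Against the planned 8 points, these are 10% (0.83/8) to 24% (1.91/8). A window centred midway between peak and trough has no shift.

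**3. Exact type I error at 135 per group.** The Pearson rejection probability was summed over both binomial distributions. Without seasonality it is 5.1%.

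| Swing | Window | 3D at trough | 3D at peak | Mean over start dates |
|---|---|---|---|---|
| 20% | 6 months | 6.6% | 6.4% | 5.8% |
| 20% | 8 months | 5.7% | 5.6% | 5.4% |
| 30% | 6 months | 8.6% | 7.9% | 6.7% |
| 30% | 8 months | 6.5% | 6.3% | 5.7% |

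The chance of a false result favouring 3D is 2.5% without seasonality. With the 3D window at the trough it rises to 5.5% (20% swing, 6 months) and 7.9% (30% swing, 6 months). At the peak the bias runs against 3D.

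**4. Attendance, as an illustration only.** The protocol gives no attendance rate. Assuming 80% with a swing of 8 points, the worst-phase shift is 8 × 0.637 = 5.1 points or 8 × 0.413 = 3.3 points. Type I error is about 10-20% at the worst start dates and 7.8-11.7% averaged over start dates.

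**5. Is there room to match?** From "10-15 vascular ultrasound tests are performed on a daily basis": 6 × 21 × 10 = 1,260 scans up to 8 × 21 × 15 = 2,520 scans. The 135 controls would be 135/1,260 = 10.7% down to 135/2,520 = 5.4% of them. These are scans, not distinct patients followed by the wound center, so the usable pool is smaller by an unknown amount.

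**The case against.** The strongest reply is that no seasonality is shown. A reader might infer that the planned comparison is seasonally biased, but the protocol holds no data on how readmission or attendance moves through the year. Existence, size and direction are all assumed here. That stands, and the point is therefore conditional.

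Three other inferences go too far:

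- **That the 3D cohort covers a single season.** Six to eight months span at least two, which is why the swing is cut to 0.637 or 0.413 of its full size.
- **That the controls will be spread over all 12 months.** Section 7 sets an eligibility window. How the 135 are drawn from it is not stated, and even spread is an assumption of the calculation.
- **That error rates of 10-20% are to be expected.** Those belong to attendance at worst-case start dates, on a rate and swing the protocol does not give. Sample size and primary analysis rest on readmission, although Section 10 lists attendance alongside it.

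It can also be said that a full-year control window estimates an annual rate and is a defensible choice, and that the regression in Section 12 could take in season, with the covariate list left to an analysis plan. Both are fair. But that adjustment is conditional, does not name month, and leaves the primary chi-square test as it is. The control window is fixed in the protocol itself and can be improved there.

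**Conclusion.** The mismatch between the windows is in the text, and nothing stated aligns them. Whether it biases the result is unknown. Under the assumed 20-30% swings and evenly spread controls, the readmission difference shifts by at most 0.8-1.9 points of the planned 8. Type I error is 5.6-8.6% at the worst start dates and 5.4-6.7% on average, against 5.1% with no seasonality; for some start dates the shift is zero. This is a secondary weakness, worth correcting because the correction is cheap. The documents do not support calling it a demonstrated bias.

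**What to change.** In Section 7, restrict the retrospective cohort to 2019 scans performed in the same calendar months as 3D enrolment, in similar monthly proportions where feasible. Because follow-up for both outcomes runs from the scan, aligning scan months aligns the time of year of the outcomes as well.

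The cost is one line of text. The number of patients stays at 135 per group and power is unchanged. It is not wholly free: the control months, and any monthly proportions, can be settled only once the 3D enrolment months are known, and the pool of eligible followed patients in those months should be confirmed first. The change removes within-year imbalance only if the seasonal pattern is similar in both years. It does nothing about the gap between 2019 and the 3D enrolment period, or about the different entry criteria of the two cohorts (consent in one, wound-center follow-up in the other).
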